### 5.2.2. Analyses for Continuous Endpoints

#### 5.2.2.1. Geometric Mean Titers

GMTs will be computed for each hSBA titer for MenB and MenACWY strains. If the hSBA result is below LLOQ, it will be set to  $\frac{1}{2}$  the LLOQ for the GMT calculation. The assay results at each blood sampling time point will be (natural-log) logarithmically transformed for analysis. GMTs are obtained by log transformations of indicated values, averaging the log values, then exponentiating the result. The associated 2-sided 95% CIs are obtained by exponentiating the limits of CIs for the mean logarithm of the hSBA titers (based on the Student t distribution).

#### 5.2.2.2. Reverse Cumulative Distribution Curves

RCDCs for MenB and MenACWY strains for a combination of available time points and Groups 1 and 2 may be generated.

### **5.2.2.3. Days Missed**

Days in which a participant missed school and/or work will be captured on the AE checklist. The data captured at each visit will be summarized and the total number of missed days of school and/or work will be obtained.

## **5.3. Methods to Manage Missing Data**

### **5.3.1. Safety Data**

Standard algorithms on handling missing AE dates will be applied according to Pfizer safety rules.

### **5.3.2. Immunogenicity Data**

As assay data are expected to be missing completely at random, the primary analysis for the primary objectives will be based upon the observed, determinate observations. No imputation will be performed. The proportion of participants with missing immunogenicity data may be summarized at each blood sampling visit for each MenB and MenACWY strain. The denominator will be the as-randomized population. The category of missing reasons (QNS, indeterminate, not done, dropout) may also be summarized.

For the hSBA assay results, the following values will be set to missing: QNS (insufficient sera), indeterminate results, and not done. Participants without blood draw (ie, dropout) will also have missing data for immunogenicity.

## **6. ANALYSES AND SUMMARIES**

### **6.1. Primary Endpoints**

#### **6.1.1. Primary Immunogenicity Endpoints**

##### **6.1.1.1. hSBA Titer for Each of the Primary MenB Test Strains (A22, A56, B24, and B44), Group 1 (0- and 12-Month Schedule)**

###### **6.1.1.1.1. Main Analysis**

- Estimand strategy: Hypothetical.
- Analysis set: Post–Vaccination 2 evaluable population for Group 1.
- Analysis methodology: Exact 2-sided 95% CIs for the percentages using the Clopper-Pearson method.
- Intercurrent events and missing data: Missing serology results will not be imputed. Participants will be summarized according to the vaccine group to which they were randomized.
- For each of the 4 primary MenB test strains, the percentage of participants with an hSBA titer  $\geq$  LLOQ at baseline and at 1 month after the second dose of MenABCWY will be calculated for Group 1 based on the post–Vaccination 2 evaluable population.

### **6.1.1.1.2. Sensitivity/Supplementary Analyses**

The main analysis will also be performed on the mITT population if there is a difference of more than 10% between the evaluable and mITT populations.

#### **6.1.1.2. hSBA Titer for Each of the Primary MenB Test Strains (A22, A56, B24, and B44), Group 2 (0- and 36-Month Schedule)**

##### **6.1.1.2.1. Main Analysis**

- Estimand strategy: Hypothetical.
- Analysis set: Post–Vaccination 2 evaluable population for Group 2.
- Analysis methodology: Exact 2-sided 95% CIs for the percentages using the Clopper-Pearson method.
- Intercurrent events and missing data: Missing serology results will not be imputed. Participants will be summarized according to the vaccine group to which they were randomized.
- For each of the 4 primary MenB test strains, the percentage of participants with an hSBA titer  $\geq$  LLOQ at baseline and at 1 month after the second dose of MenABCWY will be calculated for Group 2 based on the post–Vaccination 2 evaluable population.

##### **6.1.1.2.2. Sensitivity/Supplementary Analyses**

The main analysis will also be performed on the mITT population if there is a difference of more than 10% between the evaluable and mITT populations.

### **6.1.2. Primary Safety Endpoints**

#### **6.1.2.1. Serious Adverse Events, Medically Attended Events, and Newly Diagnosed Chronic Medical Conditions**

- Analysis set: Safety. Refer to [Section 4](#) for visit-specific populations.
- Analysis methodology: Descriptive summary statistics and Clopper-Pearson CIs.
- Intercurrent events and missing data: Participants will be analyzed according to the vaccine they actually received. Missing AE dates will be handled according to the Pfizer safety rules.
- For each group, the numbers and percentages of participants with MAEs, SAEs, and NDCMCs for the 11 analysis intervals defined in [Table 5](#) will be summarized. For the events during the vaccination phase, follow-up phase, and 6 months after Vaccinations 1 and 2, the (n), %, and 95% CI may be presented for any event, for each SOC, and for each PT within each SOC.

### **6.1.2.2. Adverse Events**

- Analysis set: Safety. Refer to [Section 4](#) for visit-specific populations.
- Analysis methodology: Descriptive summary statistics and Clopper-Pearson CIs.
- Intercurrent events and missing data: Participants will be analyzed according to the vaccine they actually received. Missing AE dates will be handled according to the Pfizer safety rules.
- For each group, the numbers of participants with AEs for the first 7 analysis intervals defined in [Table 5](#) will be summarized. The (n), %, and 95% CI may be presented for any event, for each SOC, and for each PT within each SOC.

Nonserious AEs are not required to be reported during the follow-up phase; however, if nonserious AEs during the follow-up phase were recorded in the database (excluding MAEs and nonserious NDCMCs), these data will be listed separately.

### **6.1.2.3. Immediate Adverse Events**

- Analysis set: Safety. Refer to [Section 4](#) for visit-specific populations.
- Analysis methodology: Descriptive summary statistics and Clopper-Pearson CIs.
- Intercurrent events and missing data: Participants will be analyzed according to the vaccine they actually received. Missing AE dates will be handled according to the Pfizer safety rules.
- The number and percentage of participants reporting AEs occurring within the 30-minute observation period immediately after vaccination will be summarized according to the 3 analysis intervals defined in [Table 6](#). These summaries will include 95% Clopper-Pearson CIs.

### **6.1.2.4. Days Missing School or Work**

- Analysis set: Safety. Refer to [Section 4](#) for visit-specific populations.
- Analysis methodology: Descriptive summary statistics and Clopper-Pearson CIs.
- Intercurrent events and missing data: Participants will be analyzed according to the vaccine they actually received. Missing AE dates will be handled according to the Pfizer safety rules.
- The percentage of participants with missed days of school and/or work will be descriptively summarized according to Intervals 7, 10, and 11 in [Table 5](#).

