- Intercurrent event(s): Participants will be analyzed according to the vaccine they actually received. Missing AE dates will be handled according to the Pfizer safety rules.
- Population-level summaries:
  - The percentage of participants reporting at least 1 AE, at least 1 SAE, at least 1 MAE, and at least 1 NDCMC during the following time periods:
    - 30 Days after each vaccination.
    - 30 Days after any MenABCWY vaccination.
    - During the Vaccination 1, 2, and 3 vaccination phases:
      - From Vaccination 1 (Visit 1) through 1 month after Vaccination 1 (Visit 2) in Groups 1 and 2.
      - From Vaccination 2 (Visit 4) through 1 month after Vaccination 2 (Visit 5) in Groups 1 and 2.
      - From Vaccination 3 (Visit 9) through 1 month after Vaccination 3 (Visit 10) in Group 2.
  - The percentage of participants reporting at least 1 SAE, at least 1 MAE, and at least 1 NDCMC during the following time periods:
    - During the follow-up phases:
      - From 1 month after Vaccination 1 (Visit 2) through 6 months after Vaccination 1 (Visit 3) in Groups 1 and 2.
      - From 1 month after Vaccination 2 (Visit 5) through 6 months after Vaccination 2 in Groups 1 and 2.

- 6 Months after Vaccinations 1 and 2:
  - From Vaccination 1 (Visit 1) through 6 months after Vaccination 1 (Visit 3) in Groups 1 and 2.
  - From Vaccination 2 (Visit 4) through 6 months after Vaccination 2 in Groups 1 and 2.
- The percentage of participants reporting at least 1 immediate AE after each vaccination.

For the primary safety objective to describe the safety profile of MenABCWY when administered on a 0- and 12-month and 0- and 36-month schedule as measured by days missing school or work because of AEs, the estimand has the following attributes:

- Population: Participants receiving at least 1 dose of study intervention.
- Variable: Days missing from school or work because of AEs.
- Intercurrent event(s): Participants will be analyzed according to the vaccine they actually received. Missing AE dates will be handled according to the Pfizer safety rules.
- Population-level summary: The percentage of participants who missed days of school and/or work because of AEs occurring within 6 months after Vaccinations 1 and 2 and within 1 month after Vaccination 3.

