Group 1 (0- and 12-Month Schedule)							
Visit Identifier	Visit 1	Visit 2	Visit 3	Visit 4	Visit 5	Visit 6	Visit 7 a
Visit Description	Vaccination 1	1-Month Post-Vaccination 1 Blood Draw	Safety Telephone Contact 1	Vaccination 2	1-Month Post-Vaccination 2 Blood Draw	12-Month Antibody Persistence Visit	24-Month Antibody Persistence Visit
Approximate Month	0	1	6	12	13	24	36
Visit Window	Day 1	28 to 42 Days After Visit 1	168 to 196 Days After Visit 1	336 to 394 Days After Visit 1	28 to 42 Days After Visit 4	336 to 394 Days After Visit 4	700 to 756 Days After Visit 4
(S)AE collection appropriate for the visit f	X	X	X	X	X	X	X

Abbreviations: MAE = medically attended adverse event; NDCMC = newly diagnosed chronic medical condition; PRP-OMP = polyribosyribitol phosphate oligosaccharide of *Haemophilus influenzae* type b conjugated to outer membrane protein.

Note: A safety follow-up telephone contact should occur for all participants who withdraw from the study within 6 months after any vaccination. Refer to Section 8.1.1.3 in the protocol.

- Visits 8, 9, and 10 will not be conducted for participants in Group 1.
- Ensure that the participant continues to be eligible for the study and continues to comply with contraception requirements, as appropriate.
- Observe the participant for at least 30 minutes (or longer as per local practice) after the study intervention administration for any acute reactions.
- Record nonstudy vaccinations as described in Section 6.5 in the protocol.
- Checklist includes questions regarding NDCMCs, MAEs, and missed days of school or work, as well as neuroinflammatory and autoimmune conditions, such as transverse myelitis, uveitis, optic neuritis, and multiple sclerosis.
- Please refer to Section 8.3.1 in the protocol.

Group 2 (0- and 36-Month Schedule)								
Visit Identifier	Visit 1	Visit 2	Visit 3	Visit 4	Visit 5 a	Visit 8	Visit 9	Visit 10
Visit Description	Vaccination 1	1-Month Post-Vaccination 1 Blood Draw	Safety Telephone Contact 1	Vaccination 2	1-Month Post-Vaccination 2 Blood Draw	Safety Telephone Contact 2	Vaccination 3	1-Month Post-Vaccination 3 Blood Draw
Approximate Month	0	1	6	12	13	24	36	37
Visit Window	Day 1	28 to 42 Days After Visit 1	168 to 196 Days After Visit 1	336 to 394 Days After Visit 1	28 to 42 Days After Visit 4	336 to 394 Days After Visit 4	700 to 756 Days After Visit 4	28 to 42 Days After Visit 9
Informed consent	X							
Review eligibility criteria	X							

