##### **3.1.2. Primary Safety Endpoints**

- AEs, SAEs, MAEs, NDCMCs, and immediate AEs.
- Days missing from school or work because of AEs.

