### 3.5.1.1. Analysis Intervals

There will be 11 analysis intervals for the AE data collected via CRF (Table 5). The analysis populations used for these intervals are described in detail in Section 4.

For Vaccination 1 (Visit 1), MenABCWY will be administered to participants in both Groups 1 and 2. For Vaccination 2 (Visit 4), MenABCWY will be administered to Group 1 participants; saline will be administered to Group 2 participants. For Vaccination 3 (Visit 9), MenABCWY will be administered to Group 2 participants.

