**Table 5. Analysis Intervals for AEs, SAEs, MAEs, NDCMCs, and Days Missing School or Work Because of AEs**

Interval #	Group	Analysis Interval	Analysis Population	Interval Start Date (Inclusive)	Interval Stop Date (Inclusive)	Safety Data
1	Groups 1, 2	Within 30 days after Vaccination 1	Vax 1 safety	Vax 1 date (Visit 1 for Groups 1, 2)	Vax 1 date (Visit 1 for Groups 1, 2) + 30 days	AEs, SAEs, MAEs, NDCMCs
2	Groups 1, 2	Within 30 days after Vaccination 2	Vax 2 safety	Vax 2 date (Visit 4 for Groups 1, 2)	Vax 2 date (Visit 4 for Groups 1, 2) + 30 days	AEs, SAEs, MAEs, NDCMCs
3	Group 2	Within 30 days after Vaccination 3	Vax 3 safety	Vax 3 date (Visit 9 for Group 2)	Vax 3 date (Visit 9 for Groups 1, 2) + 30 days	AEs, SAEs, MAEs, NDCMCs
4	Groups 1, 2	Within 30 days after any MenABCWY vaccination	Safety	Vax 1 date (for Groups 1, 2) or Vax 2 date (for Group 1) or Vax 3 date (for Group 2)	Vax 1 date (Groups 1, 2) + 30 days or Vax 2 date (Group 1) + 30 days or Vax 3 date (Group 2) + 30 days	AEs, SAEs, MAEs, NDCMCs
5	Groups 1, 2	Vaccination 1 vaccination phase	Vax 1 safety	Visit 1 date	Visit 2 date (or end of vaccination day)	AEs, SAEs, MAEs, NDCMCs
6	Groups 1, 2	Vaccination 2 vaccination phase	Vax 2 safety	Visit 4 date	Visit 5 date (or end of vaccination day)	AEs, SAEs, MAEs, NDCMCs
7	Group 2	Vaccination 3 vaccination phase	Vax 3 safety	Visit 9 date	Visit 10 date (or end of vaccination day)	AEs, SAEs, MAEs, NDCMCs, days missing school or work because of AEs
8	Groups 1, 2	During follow-up phase 1	Follow-up safety 1	Visit 2 date + 1, or end of vaccination date + 1 for early withdrawal participants	6 Months after Vax 1 date (Visit 3)	SAEs, MAEs, NDCMCs
9	Groups 1, 2	During follow-up phase 2	Follow-up safety 2	Visit 5 date + 1, or end of vaccination date + 1 for early withdrawal participants	6 Months after Vax 2 date	SAEs, MAEs, NDCMCs

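### Missed school or work days after the second MenABCWY dose are summarized over 183 days in Group 1 but only 28 to 42 days in Group 2, so these two percentages cannot be read side by side

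*SAP*

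**What the plan says.** SAP 3.1.2 lists "Days missing from school or work because of AEs" as a primary safety endpoint. The estimand in SAP 2.1.4 is the percentage of participants with missed days "because of AEs occurring within 6 months after Vaccinations 1 and 2 and within 1 month after Vaccination 3"; Protocol Section 3 gives the same windows. SAP 6.1.2.4 carries this out: the percentage "will be descriptively summarized according to Intervals 7, 10, and 11" of Table 5.

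Table 5 names missed days in the data column of those three intervals only. Interval 7 (Group 2, Vaccination 3 phase) reads "AEs, SAEs, MAEs, NDCMCs, days missing school or work because of AEs". Intervals 10 and 11 cover 6 months after Vaccinations 1 and 2. Intervals 5 and 6, the Vaccination 1 and Vaccination 2 counterparts of Interval 7, do not list missed days.

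The vaccination numbers do not mean the same dose in both groups. SAP 3.5.1.1 states: "For Vaccination 2 (Visit 4), MenABCWY will be administered to Group 1 participants; saline will be administered to Group 2 participants"; and "For Vaccination 3 (Visit 9), MenABCWY will be administered to Group 2 participants".

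**The concern.** The primary safety objective is to describe the safety profile of both schedules. Readers will naturally set the second MenABCWY dose on the 12-month schedule beside the second dose on the 36-month schedule. For AEs, SAEs, MAEs and NDCMCs they can do so over short windows defined alike in both groups (Intervals 2 and 3, and Intervals 6 and 7), and immediate AEs also have matched windows. Missed days are the exception: Group 1's figure runs for about 6 months and Group 2's stops at about 1 month.

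The longer window contains the shorter one, so if participants behave identically after the two second doses, Group 1's expected percentage can only be equal or higher. The longer window also mixes two levels of capture. All AEs are collected for about a month, but afterwards "Nonserious AEs are not required to be reported during the follow-up phase" unless they are MAEs or NDCMCs. No percentage is specified for the month after Group 1's second dose, when absence caused by vaccine reactions would be expected.

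**Working it through.** **Inputs**
- Interval 11 length: 183 days (note to SAP Table 5).
- Interval 7 length: Visit 9 to Visit 10, where Visit 10 falls "28 to 42 Days After Visit 9" (SAP 2.2.1).
- AE capture: all AEs for about 1 month after each vaccination; SAEs, MAEs and NDCMCs to about 6 months after Vaccinations 1 and 2 (SAP 3.5.1).
- Missed-day rate: none given in either document.

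**The plan's own figure.** 6 × 365.25 / 12 = 182.6, which rounds to the stated 183 days.

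**Windows by dose, as planned**

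| Dose | Group 1 | Group 2 |
|---|---|---|
| First MenABCWY | 6 months (Interval 10) | 6 months (Interval 10) |
| Saline | not given | 183 days (Interval 11) |
| Second MenABCWY | 183 days (Interval 11) | 28 to 42 days (Interval 7) |

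Only the last row is mismatched. Its window ratio is 183/42 = 4.4 to 183/28 = 6.5.

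**Illustration of the effect.** Assume a proportion p has a missed day by day 30, with constant hazard over that month: h = −ln(1 − p)/30. Assume that from day 30 to day 183 (153 days) the collected hazard is a fraction f of h, because fewer kinds of event are recorded. Then P(183 days) = 1 − exp[−h × (30 + 153f)].

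For p = 5%, h = 0.05129/30 = 0.001710 per day:
- f = 0.25: 1 − exp(−0.001710 × 68.25) = 11.0%
- f = 0.50: 1 − exp(−0.001710 × 106.5) = 16.6%

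Range over other assumed values:

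| By day 30 | f = 0 | f = 0.25 | f = 0.50 | f = 1 |
|---|---|---|---|---|
| 2% | 2.0% | 4.5% | 6.9% | 11.6% |
| 5% | 5.0% | 11.0% | 16.6% | 26.9% |
| 10% | 10.0% | 21.3% | 31.2% | 47.4% |

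At f = 0.25 to 0.50 with p = 5%, the longer window gives 2.2 to 3.3 times the 30-day figure (11.0/5 and 16.6/5) with the same underlying behaviour in both groups.

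**Can a short window be built from the data?** Yes. The AE checklist asks about AE-related missed days since the last visit at Visit 2, Visit 5 and Visit 10 (Protocol 8.11), and AE-related missed days go into the CRF (Protocol 8.2). For Group 1, the Visit 5 answer covers Visit 4 to Visit 5, which is Interval 6.

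**The case against.** The strongest reply is that nothing planned goes wrong. The study tests no hypotheses (SAP 5.1), no comparison of the two second doses on missed days is specified, and the windows are stated openly in the estimand. Protocol and SAP agree. The shorter window follows from Amendment 1, which cut follow-up after Vaccination 3 to 1 month when Visit 11 was removed. All of this stands, and it limits the weight of the point. It explains why Group 2 has no 6-month figure after Vaccination 3; it does not explain why Group 1 has no 1-month figure after Vaccination 2.

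SAP 5.2.2.3 also says that missed days captured at each visit will be summarized and totalled. A reader might infer that no summary at all will exist for the month after Group 1's second dose; that section does not support so strong a reading. It does not, however, specify a percentage of participants over a matched window.

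Two other stronger readings are tempting:
- A reader might infer that the two schedules cannot be compared on this endpoint at all. Interval 10 gives both groups the same 6 months after the first dose, and Interval 11 sets Group 1's second dose beside Group 2's concurrent saline over equal time.
- A reader might scale the 26.2% MAE rate from Study B1971057 (Protocol 2.2.2.3) to a nearly 6-fold difference. That essentially restates the ratio of the window lengths. The rate comes from MenABCWY recipients over a period that includes the month after each dose, so it is not a background rate, and it omits the non-attended AEs collected in month 1, which understates the short-window figure.

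**Conclusion.** The point holds for one contrast: missed days after the second MenABCWY dose, 183 days in Group 1 against 28 to 42 days in Group 2. The two percentages should not be read side by side. The window ratio of 4.4 to 6.5 follows directly from the documents. The 11-17% against 5% is an illustration resting on an assumed 30-day rate, a constant hazard within each period and an assumed fall in the collected hazard; the true size is unknown.

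This is a limit on interpretation in a descriptive study. It is not an error in a test or a departure of the SAP from the protocol, and the priority is low. Equal windows would not remove every difference: Group 2's second dose is open-label and given about 2 years later (Month 36 against Month 12), at an older age.

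**What to change.** - Add missed days to the data column of Table 5 for Intervals 5 and 6, and have SAP 6.1.2.4 report Intervals 5, 6 and 7 together. Every dose, including saline, then has a percentage over a vaccination phase of 28 to 42 days. These windows end at a visit, so they are only approximately equal.
- If exactly equal windows are wanted, use the fixed 30-day Intervals 1 to 3 instead.
- Keep Intervals 10 and 11, which the estimand requires, as the longer-term summary. Add a footnote that after month 1 they are limited to SAEs, MAEs and NDCMCs.

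The cost is two more intervals in an existing table and one footnote. The data are already collected on the checklist, and the estimand is unchanged.

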## **6.2. Secondary Endpoints**

### **6.2.1. Secondary Immunogenicity Endpoints**

#### **6.2.1.1. hSBA Titer for Each of the MenACWY Test Strains**

##### **6.2.1.1.1. Main Analysis**

- Estimand strategy: Hypothetical.
- Analysis set: Post-Vaccination 1 and Post-Vaccination 2 evaluable populations for Groups 1 and 2.
- Analysis methodology: Exact 2-sided 95% CIs for the percentages using the Clopper-Pearson method.
- Intercurrent events and missing data: Missing serology results will not be imputed. Participants will be summarized according to the vaccine group to which they were randomized.
- The percentage of participants in Group 1 (0- and 12-month schedule) and Group 2 (0- and 36-month schedule) separately and combined with hSBA titers  $\geq$  LLOQ for each of the ACWY test strains at baseline and at 1 month after the first dose of MenABCWY may be summarized using the post-Vaccination 1 evaluable population. The percentage of participants in Groups 1 and 2 separately with hSBA titers  $\geq$  LLOQ for each of the ACWY test strains at baseline and at 1 month after the second dose of MenABCWY will be summarized using the post-Vaccination 2 evaluable population.

##### **6.2.1.1.2. Supplemental Analysis**

The main analysis will also be performed on the mITT population if there is a difference of more than 10% between the evaluable and mITT populations.

#### **6.2.1.2. hSBA Titer for Each of the Primary MenB Test Strains (A22, A56, B24, and B44), Group 1 (0- and 12-Month Schedule)**

##### **6.2.1.2.1. Main Analysis**

- Estimand strategy: Hypothetical.
- Analysis set: Post-Vaccination 2 evaluable population for Group 1.
- Analysis methodology: Exact 2-sided 95% CIs for the percentages using the Clopper-Pearson method.
- Intercurrent events and missing data: Missing serology results will not be imputed. Participants will be summarized according to the vaccine group to which they were randomized.

- The percentage of participants in Group 1 (0- and 12-month schedule) with hSBA titers  $\geq$  LLOQ for each of the primary MenB test strains at 12 and 24 months after the second dose of MenABCWY will be summarized using the post-Vaccination 2 evaluable population.

